11.4.1. Analysis of the primary endpoint(s)

The primary efficacy endpoint is *NACE*, i.e., the composite of all-cause death, MI, ischemic stroke, SEE, valve thrombosis, and major bleeding (ISTH definition).

The primary safety endpoint is *major bleeding (ISTH definition)*.

There are 4 primary hypotheses that will be tested in hierarchical order:

- Hypothesis (1):
 - The Edoxaban-based regimen is noninferior to the VKA-based regimen with regards to NACE.
- Hypothesis (2):
 - The Edoxaban-based regimen is noninferior to the VKA-based regimen with regards to major bleeding (ISTH definition).
- Hypothesis (3):
 - The Edoxaban-based regimen is superior to the VKA-based regimen with regards to major bleeding (ISTH definition).
- Hypothesis (4):
 - The Edoxaban-based regimen is superior to the VKA-based regimen with regards to NACE.

The analysis set and analysis periods to be used for the main analysis related to these four hypotheses are presented below:

Table 11.1: Statistical Analysis Hierarchy for Primary Parameters

Hypothesis	Endpoint	Primary Analysis Set	Primary Analysis Period
(1)	NACE	ITT	Overall study period
(2)	Major bleeding (ISTH def)	ITT	Overall study period
(3)	Major bleeding (ISTH def)	ITT	Overall study period
(4)	NACE	ITT	Overall study period

To control the type-I error rate, these four hypotheses will be tested in a hierarchical manner:

- Step (1): The Edoxaban-based regimen will be considered noninferior to the VKA-based regimen with regards to NACE, if the upper boundary of the two-sided 95% CI for hazard ratio (HR) falls below 1.38. If it is significant, then go to Step (2), otherwise stop here.
- Step (2): The Edoxaban-based regimen will be considered noninferior to the VKA-based regimen with regards to major bleeding (ISTH def.), if the upper boundary of the two-sided 95% CI for HR falls below 1.38. If it is significant, then go to Step (3), otherwise stop here.
- Step (3): The Edoxaban-based regimen will be considered superior to the VKA-based regimen with regards to major bleeding (ISTH def.), if the upper boundary of the two-sided 95% CI for HR falls below 1.00. If it is significant, then go to Step (4), otherwise stop here.
- Step (4): The Edoxaban-based regimen will be considered superior to the VKA-based regimen with regards to NACE, if the upper boundary of the two-sided 95% CI for HR falls below 1.00.

For each of the primary and secondary adjudicated endpoints, appropriate summary statistics (e.g., event rate) including 95% CI will be provided.

For each of the adjudicated endpoints, the time from reference date to the first occurrence of an event (based on CEC adjudication), is analyzed using a Cox proportional hazard model with treatment regimen as a factor and all the stratification factors from the randomization (IXRS) [dose adjustment [yes, no]] as covariates, to provide point estimates and 95% Confidence Interval (CI) for the hazard ratio (HR). Depending on the analysis period used in the statistical analysis, subjects without an occurrence of an event

will be censored at the last date of the analysis period or at the last date of known outcomes status. The latter is determined an individual basis for subjects with incomplete follow-up.

To evaluate the robustness of the primary analyses, the analyses will be repeated using the mITT and PP analysis set. In addition, the statistical results based on the following analysis periods: 'initial dose to final dose + 30 days' and 'overall study period + 30 days' will be presented and will be interpreted in a more descriptive way. Results for other combinations of analysis sets and analysis periods may be presented if considered necessary.

For time to first event analyses based, cumulative event rates over time are summarized using the Kaplan-Meier method as appropriate.

11.4.2. Analyses of the secondary exploratory endpoints

The main analyses for all secondary efficacy and safety endpoints will be based on first occurrence of an (adjudicated) endpoint during the 'overall study period' for all subjects belonging to the ITT analysis set and applying the aforementioned statistical method.

There will be no formal statistical testing for secondary exploratory endpoints. HRs, CI and p-values are provided but should be interpreted in a purely descriptive exploratory manner.

To evaluate the robustness of the main analyses, the analysis will be repeated using the mITT and PP analysis set. In addition, the statistical results based on the following analysis periods: 'initial dose to final dose + 30 days' and 'overall study period + 30 days' will be presented but should be interpreted as supportive. Results for other combinations of analysis sets and analysis periods may be presented if considered necessary.

11.4.3. Pharmacokinetic/Pharmacodynamic Analyses

11.4.3.1. Pharmacokinetic Analyses

Not applicable.

11.4.3.2. Pharmacodynamic Analyses

Not applicable.

11.4.3.3. Biomarker Analyses

A potential sub-study is possible which will have a separate analysis plan.

11.4.3.4. Pharmacogenomic Analyses

Not applicable.

11.4.4. Health Economics Outcome Research (HEOR) Analyses

For healthcare resource utilization, proportion of subjects with hospitalization, number of hospitalizations, and length of hospital stay related to cardiovascular events of protocol

interest during the study will be described using summary statistics and compared between treatments.

For the PACT-Q, the absolute PACT-Q1 item scores and change from baseline values at the 12 months (or end of treatment if earlier) will be described using summary statistics and compared between treatments. In addition, the PACT-Q2 Convenience and Treatment Satisfaction scores will be summarized at each scheduled time point (Table 17.1) and compared between treatment groups.

For the EQ-5D-5L, the absolute and change from baseline values for the five domain scores, the EQ-5D-5L index value, and the EQ VAS score will be described using summary statistics by scheduled time point and compared between treatments.

Additional details will be provided in the SAP.

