6.2. Randomization Visit (Day 1)

Randomization must take place within the evening of the day of TAVI and 5* days, i.e., until 23:59 of the 5th* day provided that the TAVI procedure has been judged as successful (See inclusion criteria #1 for definition of successful TAVI), and the subject is qualified based on all the protocol defined inclusion/exclusion criteria. Randomization should occur as soon as possible after signing the informed consent, given eligibility is confirmed.

*If subject is waiting on a decision on pacemaker surgery, then can extend to 7 (7th) days

- Check subject against inclusion/exclusion criteria including the most recent lab results.
- Record type of TAVI device inserted into subject in the eCRF

- Enter elements for EuroSCORE 1, EuroSCORE 2, Society of Thoracic Surgeons (STS), CHAD, and HAS-Bleed scores into the eCRF
- Contact IXRS for randomization and pre-declaration of OAP.
- Prior to any study drug administration or other tests, the subject must complete the PACT-Q1 and EuroQoL (EQ-5D-5L) questionnaires. These will be collected and uploaded into the data base by the CRO via the eCRF.
- If ECG was performed as part of routine medical practice, record the results. If not obtained as part of routine medical practice, collect a pre-dose ECG for baseline measurement and record results.
- Update medical / surgical history (including bleeding history) since screening
- Physical Examination including
 - Record vital signs (blood pressure and heart rate after the subject has been resting at least 5 minutes in a sitting position; body temperature, and weight)
 - Record height
- Record prior (since screening) medications and review as per exclusion criteria.
- If echocardiogram (transthoracic echo [TTE] or transesophageal echo [TEE]) was performed pre-TAVI per local standard of care, the information will be recorded as specified in the eCRF.

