10.3. EuroQoL (EQ-5D-5L) Questionnaire

The EQ-5D-5L is standardized measure of health status developed by the EuroQoL Group in order to provide a simple descriptive profile and a single health status index. The EQ-5D-5L consists of two measures: 1) the EQ-5D-5L descriptive system and 2) the EQ Visual Analogue Scale (EQ VAS). The EQ-5D-5L descriptive system asks the subject to provide rating on each of the five dimensions of health: mobility, self-care, usual activities, pain/discomfort and anxiety/depression. The EQ VAS records the subject's overall health on a 0 to 100 analogue scale anchored from "best imaginable health state" to "worst imaginable health state".

The EQ-5D-5L is designed for self-completion by study subjects and takes only 1 to 2 minutes to complete. The EQ-5D-5L will be administered for study subjects at randomization, 3 months and either 12 months or the EOT whichever comes first. A copy of the EQ-5D-5L will be provided to the sites.

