11.2. General Statistical Considerations

All analyses will be performed on observed data only. No missing data will be imputed. Data on subjects who do not reach a specific endpoint will be censored in the corresponding statistical analyses.

Raw data will be presented with the exact precision (decimal points) with which it was collected.

The p-values will be presented in the end-of-text tables exactly as they are in supporting statistical documents (4 decimal points). The text and in-text tables will display p-values with three decimal places, as long as the decision for statistical significance will not be changed by rounding.

The number of decimal places to display for calculated data will be determined by the scale of measurement. No decimal places will be displayed if the smallest calculated value is ≥ 100 ; one (1) decimal place will be displayed when all calculated values are within the interval (10, 100), with 10 being inclusive; two (2) decimal places will be displayed when all calculated values are within (1, 10), with 1 being inclusive; and so on for even smaller scales of measurement. Percentages will be reported with exactly one decimal place.

For continuous variables, statistical summaries will include n (number of subjects with non-missing data), mean, median, standard deviation, minimum, and maximum. Means and medians will be displayed to one more decimal places than the raw or calculated data; standard deviation and other dispersion statistics will have two more decimal places; and minimum and maximum values will be displayed to the same number of decimal places as the raw or calculated data.

For categorical variables, statistical summaries will include counts and percentages. Percentages will be reported with exactly one decimal place. In general, percentages are based on the total number of subjects with information available (i.e., non-missing data). For AE and incidence-based analyses, percentages will be based on the total number of subjects in the analysis set of interest and in that treatment regimen.

Definition of terms:

'Overall Study Period': This period is defined as the time from the reference date up to an estimated Month 36/EOT (Visit 8).

'Overall Study Period + 30 days': This period is defined as the time from the reference data up to an estimated Month 36/EOT (Visit 8) + 30 days, i.e., to Month 37 (post-treatment FU visit).

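### The EQ-5D-5L comparison names no baseline-adjusted model although a baseline is collected; adjusting would cut variance against change scores by 15–30% if the baseline correlation is 0.4–0.7 (assumed)

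*Combined protocol and SAP*

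**What the plan says.** Section 11.4.4 lists what is to be analysed for EQ-5D-5L: "the absolute and change from baseline values for the five domain scores, the EQ-5D-5L index value, and the EQ VAS score". These "will be described using summary statistics by scheduled time point and compared between treatments". No test, model or covariate is named, and nothing says which of the two comparisons, absolute or change, is the one to read. The section closes with "Additional details will be provided in the SAP". No SAP text for this endpoint is in the supplied document.

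The baseline form precedes treatment. Section 6.2 states: "Prior to any study drug administration or other tests, the subject must complete the PACT-Q1 and EuroQoL (EQ-5D-5L) questionnaires". Section 10.3 sets the collection schedule: "The EQ-5D-5L will be administered for study subjects at randomization, 3 months and either 12 months or the EOT whichever comes first".

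Section 11.2 gives the general rule on missing data: "All analyses will be performed on observed data only. No missing data will be imputed".

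Section 7.4.3 lists EQ-5D-5L among the other endpoints, outside the four hierarchical hypotheses. The synopsis (Statistical Analyses) plans no formal testing of such endpoints.

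**The concern.** When a baseline is measured on everyone before treatment in a randomised trial, there are three usual ways to compare arms at follow-up: the absolute value, the change from baseline, or the follow-up value adjusted for baseline in a regression. The first ignores the baseline. The second subtracts all of it, which over-corrects when the baseline predicts follow-up only in part. The third estimates how much to subtract. Section 11.4.4 names the first two and is silent on the third.

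Two things are at stake. One is precision: the interval for the quality-of-life difference may be wider than the collected data require. The other is clarity: chance baseline differences can make the absolute and change comparisons disagree, and the plan does not say which would then be reported as the result. Neither touches the primary hypotheses.

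**Working it through.** The plan states no figure for this endpoint (no standard deviation, correlation, effect size or power), so there is nothing to reproduce. The check is of relative precision only.

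**Inputs**
- Quantities compared: absolute and change values (Section 11.4.4).
- Baseline available before study drug: yes (Section 6.2).
- Subjects: about 1400 randomised 1:1, hence about 700 per arm (Section 11.9). This is used only for the simulation check.
- rho, the correlation of baseline with follow-up: not given. Assumed 0.4–0.7.
- k, the follow-up SD divided by the baseline SD: not given. Assumed 1, then varied from 0.8 to 1.25.

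**General form.** Put the baseline SD at 1. Comparing arms on (follow-up − b × baseline) has variance proportional to k² + b² − 2·b·rho·k. The absolute comparison is b = 0 and the change comparison is b = 1. The minimum is at b = rho·k, where the variance is k²(1 − rho²). In large samples a linear model with baseline as covariate estimates that b, so it cannot be less precise than either planned comparison.

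**Equal SDs (k = 1).** The relative variances are:
- absolute: 1
- change: 2(1 − rho)
- adjusted: 1 − rho²

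Hence adjusted/change = (1 − rho²) / [2(1 − rho)] = (1 + rho)/2, and adjusted/absolute = 1 − rho².

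| rho | change/absolute | adjusted/change | variance reduction vs change | SE reduction vs change | adjusted/absolute |
|---|---|---|---|---|---|
| 0.4 | 1.20 | 0.70 | 30% | 16.3% | 0.84 |
| 0.5 | 1.00 | 0.75 | 25% | 13.4% | 0.75 |
| 0.6 | 0.80 | 0.80 | 20% | 10.6% | 0.64 |
| 0.7 | 0.60 | 0.85 | 15% | 7.8% | 0.51 |

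The change score is less precise than the absolute score below rho = 0.5 and more precise above it. Neither planned comparison is therefore the better one across the range. Against the absolute score, the adjusted variance is lower by 16% (rho 0.4) to 49% (rho 0.7).

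**Simulation check.** With 700 per arm and 4000 replicates, adjusted/change was 0.705 at rho 0.4 and 0.860 at rho 0.7 (formula 0.70 and 0.85). Adjusted/absolute was 0.820 and 0.521 (formula 0.84 and 0.51).

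**Unequal SDs.** Adjusted/change = k²(1 − rho²) / (k² + 1 − 2·rho·k).
- k = 0.8, rho = 0.4: 0.64 × 0.84 / (0.64 + 1 − 0.64) = 0.538, a reduction of about 46%.
- k = 1.25, rho = 0.7: 1.5625 × 0.51 / (1.5625 + 1 − 1.75) = 0.797/0.8125 = 0.981, a reduction of about 2%.

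So the 15–30% depends on equal SDs as well as on rho. Over the wider grid the reduction runs from about 2% to 46%.

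**The case against.** The strongest reply is that Section 11.4.4 does not specify an unadjusted comparison. It names quantities, not a method, and leaves the detail to the SAP. A linear model of change from baseline with baseline as a covariate would fit its wording and give exactly the same treatment estimate as the adjusted follow-up value. This stands: the plan omits the better method but does not rule it out. It does not dispose of the point. The protocol already names the quantities to be compared, and Section 11.10 requires the SAP to be final only before database lock, in an open-label trial. Naming one comparison now costs nothing.

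It can also be said that little depends on the endpoint. That stands as well, and it limits the weight of the point.

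Three stronger readings are tempting, and the documents do not support them.
- A reader might infer that the baseline is wasted. It is not: change scores use it, though inefficiently. Only the absolute comparison ignores it.
- A reader might infer that an early end-of-treatment form is analysed as a 12-month value. Section 10.3 and Table 17.1 say when forms are collected. The explicit pooling of 12 months with an earlier end of treatment in Section 11.4.4 is in the PACT-Q sentence. For EQ-5D-5L the text says only that analysis is by scheduled time point.
- A reader might infer a stated plan to drop deaths, or that the index must be set to 0 at death. That deaths fall out follows from the general rule in Section 11.2 and is not stated for EQ-5D-5L. The documents give no value for death, and assigning one is a debatable choice of estimand. All-cause mortality is in any case reported as its own endpoint (Section 7.4.2).

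**Conclusion.** The point holds as a no-cost improvement to an exploratory analysis. It is not an error that threatens a conclusion.

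The direction needs only large samples and a linear model with an estimated baseline coefficient. The size rests on two assumptions outside the documents: rho of 0.4–0.7 and equal SDs at the two times. The 15–30% should be read as a reduction in variance, or equivalently in the number of subjects needed for the same precision. It should not be read as the narrowing of the confidence interval, which is 8–16%, nor as relative efficiency, which on the same inputs is 18–43% (1/0.85 − 1 to 1/0.70 − 1).

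Under "All analyses will be performed on observed data only", whichever comparison is used describes subjects who completed the form. Baseline adjustment does not alter that, so the result needs the deaths beside it to be read properly.

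**What to change.** In Section 11.4.4, or in the SAP section to which it defers:

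- Make the between-arm comparison of the EQ-5D-5L index and of the EQ VAS, at each scheduled time point, a linear model with treatment, the baseline value and the randomization stratum (dose adjustment yes/no, as in the Cox models of Section 11.4). Report the adjusted difference with its 95% CI.
- Keep absolute and change values as descriptive summaries by arm. The five domain scores can stay with descriptive summaries; the model is meant for the index and the VAS.
- Show the number of forms analysed and the number of deaths by arm at each time point beside the estimate. An analysis that assigns a value after death is optional, as a sensitivity analysis with the chosen value stated in advance.

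The cost is a few sentences and a few program lines. No new data, visits or subjects are needed, and the primary analysis and its hierarchy are untouched.

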11.5. Safety Analyses

All safety analyses described in this section will be based on the Safety analysis set.

11.5.1. Adverse Event Analyses

Adverse events meeting the criteria defined in Section 9.3 will be recorded in the eCRF and coded by system organ class and preferred term using the Medical Dictionary for Regulatory Activities (MedDRA), version 19.1 or newer.

Treatment-emergent adverse events (TEAEs) are defined as events which start on or after any first dose of the assigned study medication regimen or started prior to but then worsened after any first dose of the assigned study medication regimen. An AE that occurs more than 30 days after the date of the last dose of the assigned study medication regimen will not be counted as a TEAE.

TEAEs will be summarized by treatment group. The incidence of TEAEs will be presented by treatment group, by relationship to the assigned study regimen, and by severity. If more than one AE is coded to the same preferred term for the same subject, the subject will be counted only once for that preferred term using the greatest severity and strictest causality for the summarization by severity and causal relationship. Frequent TEAE (reported by at least 5% of subjects in any treatment group) will be summarized by regimen group.

The incidence of death, SAEs, drug-related SAEs, and AEs leading to permanent discontinuation of the assigned study regimen will be summarized. All AEs meeting the criteria defined in Section 9.3.4 will be included in a data listing and a listing to display the coding of AEs will be prepared as well.

11.5.2. Clinical Laboratory Evaluation Analyses

The clinical laboratory evaluations for each scheduled test will be summarized descriptively by treatment regimen and visit (including changes from baseline). The baseline value is defined as the last non-missing value before first administration of study medication. In addition, descriptive statistics will also be presented for the maximum and minimum post baseline values (including changes from baseline). Shift tables (in

categories of low, normal, and high) will be provided for each treatment regimen for selected laboratory parameters. Also, the number and percentage of subjects with clinically relevant abnormal laboratory values while on study drug will be calculated for each treatment regimen for selected laboratory parameters. All abnormal laboratory values will be presented in a listing.

More details will be outlined in the SAP.

11.5.3. Vital Sign Analyses

Vital signs at each evaluation point and the change from baseline will be summarized by treatment regimen. The baseline value is defined as the last non-missing value before first administration of study medication. In addition, descriptive statistics will also be presented for the maximum and minimum post baseline values (including changes from baseline).

More details will be outlined in the SAP.

11.5.4. Physical Examination Analyses

A physical examination (Section 9.12) will be performed at the Randomization Visit, End of Treatment Visit, and the Post-treatment FU Visit. The physical examination findings will be summarized by treatment regimen based on the SAF analysis set.

More details will be outlined in the SAP.

11.5.5. Electrocardiogram Analyses

The ECG evaluations at baseline and at all post baseline visits including the FU visit will be summarized by treatment regimen based on the SAF analysis set.

More details will be outlined in the SAP.

11.6. Other Analyses

If applicable, details on other analyses will be provided in the SAP.

11.7. Interim Analyses

Not applicable.

11.8. Data and Safety Monitoring Board (DSMB)

There will be an independent DSMB to protect the rights, safety and well-being of subjects participating in this study. The DSMB will be involved in the management of this clinical study serving as the safety monitoring advisory group for the study. The primary role of the DSMB will be to examine the safety data on an ongoing manner and to alert the Executive Committee in case of any clinically concerning safety issues.

The frequency and extent of the data reviews by the DSMB, details about the reviews and stopping rules or criteria for evaluating need for study protocol modifications will be described and specified in the DSMB Charter.

